3.7.2 Treatment Applicator

The PEMF system delivers pulsed RF energy to the desired treatment area via a spiral antenna in the treatment applicator. The treatment applicator contains a therapy emitter, an antenna matching circuit, and an RF therapy measuring circuit. The RF therapy measuring circuit automatically detects the level of RF signal that is radiated from the treatment applicator and sends this information to the controller for the RF generator. This feedback circuit is used to regulate the RF therapy level, as the RF circuit reactance changes due to changes in body load capacitance. In this way, the correct energy output is constantly monitored, regulated, and maintained at the preset therapy dose levels.

Subjects randomized to active treatment will receive treatment consisting of a pulse duration of 42 ± 4 microseconds, repeated every 1000 ± 25 microseconds, resulting in an output duty cycle of 4.2%, and requiring an average RF forward power level of <3 watts. The energy is transferred via cable and emitted by the radiator located on the treatment applicator circuit board for the preset 30-minute duration of therapy.

Pulse rate, pulse width, and therapy session duration are regulated by the digital control component of the RF circuit board sub-assembly. If the RF therapy measuring circuit in the treatment applicator detects an absent or out of range therapy dosage level, treatment will not occur and a "Service Required" message will be displayed on the LCD screen. In such an event, the research center will trouble shoot the issue as instructed in the Instruction Manual which accompanies the study device, and if unsuccessful in resolving the matter, will contact the sponsor to access a replacement device.

3.8 Logistics and Device Accountability

The study device will be shipped via courier (FedEx) delivery or hand delivered when possible to the investigator or designee at regular intervals or as needed during the study. The investigator or delegate will ensure that all study devices are stored in a secured area, in accordance with applicable regulatory requirements.

Study device accountability will be overseen by the site study coordinator or other delegated staff member. These records should contain the dates, quantities of devices received by the investigator, dispensed to specified subjects, or returned to sponsor. These inventories, along with shipment receipts must be made available for inspection by the sponsor or designees and all regulatory agency inspectors. At the conclusion of the study, photocopies of all study device accountability records must be provided by the site to the sponsor.

3.9 Labeling

The label on each study device kit will contain the protocol number and kit number. There will be sufficient space for study personnel to write the subject number, date dispensed, and the initials of the dispenser on the distribution label.

3.10 Preparation and Administration

Each subject will receive one device with two applicator pads to use during the study. Each treatment session with the study device will be 30 minutes in duration. All treatment sessions will be self-administered by the subject or his/her family or caregiver in the home or similar setting.

The first treatment with the study device will be administered on the morning of the day following the Enrollment Visit (Day 1) at 8am (\pm 2 hours). Subjects will assume a comfortable position, remove shoes and socks, and place one foot on each treatment applicator of the PEMF device, centering the applicators under the plantar surface (bottom of foot) of each foot as identified by the investigator. Treatment will be administered continuously for 30 minutes on both feet simultaneously. Thereafter, subjects will self-administer treatments twice daily, at 8am (\pm 2 hours) and 8pm (\pm 2 hours) up to Day 120 (4 months).

Prior to initiation of each treatment session, the subject will place the midfoot of each foot over the starburst of each applicator pad. Further directions for use for the PEMF system are found in the Instruction Manual. Upon completion of the treatment session, the subject will store the PEMF device until the time of the next scheduled treatment session.

3.11 Blinding

This is a randomized, double-blind, sham-controlled study. The sham devices will be Provant devices that are de-activated such that no RF energy is generated or delivered when the device is started. All other functions, including the start sequence, display lights, audible start-beep and operation of the sham devices are identical to that of the active Provant devices. Sham devices are indistinguishable from the active Provant devices being used in the study. The subjects and research personnel will be fully blinded to the randomization assignment and unable to differentiate active and sham devices. All research personnel at the investigative sites and sponsor will be blinded.

3.12 Study Assessments

All efficacy outcome measures will be assessed in order to allow for characterization of the response to PEMF therapy.

3.12.1 Primary Efficacy Assessment

Pain Intensity (PI)

The primary outcome measure is the absolute change in pain intensity as measured by patient reported numeric pain rating scale (NPRS) evaluations. The NPRS is a validated 11-point numerical rating scale for pain (0=no pain to 10=worst possible pain) collected as patient-reported outcomes in an electronic diary. The NPRS will be scored daily (8am \pm 2 hours) during the 14-day run-in period in order to establish a baseline for purposes of eligibility assessment. During the subsequent 4-month (120-day) treatment period, NPRS will be scored immediately after each morning treatment session (8am \pm 2 hours).

Subjects will be instructed to "Select the one number that best indicates the average intensity of pain you have had over the last 24 hours in your legs".

The primary endpoint is the absolute change from baseline in the NPRS Pain score through Month 4 (Day 120) comparing the PEMF group to the sham group. For purposes of statistical analysis, the baseline NPRS will be the average NPRS during the 7 days preceding the start of treatment with the study device. For subsequent time points, including the primary endpoint at Day 120, NPRS will be calculated as 7-day rolling averages during the treatment period.

During Part B of the protocol (through Month 12 (day 360)), NPRS will be scored immediately after each morning treatment session ($8am \pm 2$ hours) for one week prior to Months 6, 8, 10, and 12. Evaluation of the NPRS during Part B of the protocol will be considered an exploratory endpoint.

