Table 1. Classification for diabetic neuropathies

Diabetic distal symmetric peripheral neuropathy (DSPN) is the most common form of diabetic neuropathy and accounts for approximately 75% of diabetic neuropathies.³ Clinical presentation and clinical course of diabetic neuropathy varies in prevalence associated with both the duration of

disease and maintenance of adequate glycemic control. Corresponding to length dependent nerve damage, patients present with distal symptoms that progress proximally affecting the lower extremities more prominently than the upper extremities. Patients typically describe DSPN symptoms in terms of increased or decreased sensations resulting from damage of the myelinated and unmyelinated cutaneous nerve fibers.

The clinical presentation of DSPN initially involves the feet. DSPN leads to balance issues, causing fall and fractures. Initially affects smaller unmyelinated fibers which convey pain and unpleasant temperature sensations. With progression, larger myelinated fibers are affected and can be the cause of numbness, tingling, and insensate feet leading to diabetic foot ulceration (Table 2).³

Large myelinated nerve fibers	Small myelinated nerve fibers	
Numbness	Pain:	
Tingling	burning	
Poor balance	electric shocks	
	stabbing	

Table 2. Symptoms and Signs of DSPN*

*Adapted from Pop-Busui, R, Boulton, AJ. Diabetic Neuropathy: A Position Statement by the American Diabetes Association. Diabetes Care 2017 Jan; 40(1):139³

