3.4 Eligibility Criteria

Eligibility for participation in this study will be based on the inclusion/exclusion criteria. An individual subject may only be included in the study once.

Inclusion Criteria

- 1. Subject has documented Type 1 or Type 2 diabetes mellitus according to the ADA criteria (Appendix B).³³
- 2. Subject has daily pain attributed to symmetrical lower extremity diabetic peripheral neuropathy for at least 6 months prior to screening. Confirmed by score of ≥ 6 on the Toronto Clinical Neuropathy Scoring System.
- 3. Subjects' average lower extremity pain related to diabetic peripheral neuropathy over the preceding 24 hours is ≥4 and <9 based on the 11-point NPRS (0-10) at the Screening Visit.
- 4. Subject age is greater than or equal to 22 years and less than 80 years of age.
- 5. Subject is on stable diabetes treatment which should include medication and/or diet and exercise for at least 3 months prior to Screening.
- 6. Subject has an HbA1c $\leq 10\%$ at Screening or within 3 months of Screening.
- 7. Subject has not changed their analgesic prescriptions in the preceding one month.
- 8. Subject has an ankle-brachial index (ABI) of ≥ 0.8 to ≤ 1.3 . If the subject has incompressible vessels, a toe brachial index of 0.8 to 1.3 is required. These adequate lower extremity studies are with no documented intermittent claudication.
- 9. Subject walks independently with or without assistive devices, and does not require a wheel chair.
- 10. Subject is willing and able to give written informed consent and to comply with all parts of the study protocol.

- 11. Female subjects must be post-menopausal, surgically sterile, abstinent, or, if of childbearing potential, practicing (or agreeing to practice) an effective method of birth control if they are sexually active for the duration of the study. Effective methods of birth control include prescription hormonal contraceptives, intrauterine devices, doublebarrier methods, and/or male partner sterilization.
- 12. Subject can access an internet browser in the home environment or through a smart phone.

Enrollment Visit Inclusion Criteria

- 1. Average diabetic peripheral neuropathic pain intensity (NPRS score) is ≥ 4 and < 9 calculated as the mean of the daily NPRS scores for neuropathic pain in the lower extremities over the 7 days preceding the visit.
- 2. Subject has completed a minimum of 70% of the ePRO assessments during the run-in period.

Exclusion Criteria

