Subjects will be instructed to utilize their prn analgesic medications prescribed prior to enrollment in the event their diabetic neuropathy pain increases during the trial, and not to introduce new medications or therapies into their analgesic treatment regimen through Month 6 (Day 180) of the trial. In this context, "analgesic medications" includes but is not limited to nonsteroidal anti-inflammatory agents, anti-depressants and muscle relaxants, and includes medications taken on an "as needed" (prn) basis (including over the counter medications) as well as those medications taken on a regular schedule.

4.2 14-Day Run-In Period

The subject will be instructed to record NPRS scores at 8 am (\pm 2 hours) for 14 consecutive days beginning the day following the Screening Visit. There will be 2 questions generated on a daily basis, one question will address diabetic neuropathy pain and a separate question will ask the subject to enter consumption (number of pills/tablets/capsules) of each indicated analgesic taken for their neuropathic pain over the previous 24 hours.

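### The diary item behind the primary endpoint asks about pain in the legs without naming diabetic neuropathy or saying whether the feet count, although the protocol describes the same score as neuropathic pain in the lower extremities.

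*Protocol*

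**What the plan says.** Protocol section 3.12.1 (Primary Efficacy Assessment) quotes the instruction put to the subject: choose the number for the "average intensity of pain you have had over the last 24 hours in your legs". These daily ratings supply the baseline (the mean of the 7 days before treatment) and the 7-day rolling means up to Day 120. They therefore feed the primary endpoint, the responder endpoint and time to response.

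Three other places describe the pain more narrowly:

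- **Section 3.4, Enrollment Visit Inclusion 1.** The qualifying score is "calculated as the mean of the daily NPRS scores for neuropathic pain in the lower extremities over the 7 days preceding the visit". These are the run-in diary ratings.
- **Section 4.2 (14-Day Run-In Period).** Of the two daily questions, "one question will address diabetic neuropathy pain and a separate question will ask the subject to enter consumption" of analgesics taken for neuropathic pain.
- **Section 3.4, Inclusion 3.** The Screening Visit rating is "average lower extremity pain related to diabetic peripheral neuropathy over the preceding 24 hours". The words put to the subject at that visit are not given.

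On location, section 1 says: "The clinical presentation of DSPN initially involves the feet". Section 3.10 has subjects place their feet on the device, "centering the applicators under the plantar surface" of each foot.

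The SAP defines the endpoint as change in NPRS (sections 3.1.1 and 11) and does not reproduce the item.

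**The concern.** The protocol describes one score in two ways. Where it sets entry rules and procedures, the score is neuropathic pain in the lower extremities. Where it gives the words the subject answers, there is no attribution to neuropathy and the only body region named is the legs.

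Two kinds of error could follow. First, a cramp, a strain or a new injury during the 120 days would properly be included in an answer to the item as worded, although it is not the pain the device is meant to treat. Second, a subject whose pain is mainly in the soles might take the legs to exclude the feet and under-report.

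The item determines the enrollment gate (at least 4 and below 9), the baseline, the primary endpoint and the first two secondary endpoints. The indication is diabetic neuropathic pain, so the question that carries the primary result should ask about that pain.

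**Working it through.** **Step 1. Compare the descriptions of the pain score.**

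| Place in the protocol | Attributed to diabetic neuropathy? | Region |
|---|---|---|
| 3.12.1, diary item as quoted | No | Legs |
| 3.4, Enrollment Inclusion 1 (same diary scores) | Yes, neuropathic | Lower extremities |
| 4.2, run-in question (same diary) | Yes | Not stated |
| 3.4, Inclusion 3 (Screening rating, item not given) | Yes | Lower extremities |
| 3.12.2, PGI questions 1 and 3 | Yes | Legs |

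The first three rows concern the same daily diary score and do not agree on attribution. The PGI row shows that the protocol can use the legs as its everyday term for the affected region, and that it names the neuropathy when it does so. The missing attribution is therefore the firmer part of the point, and the foot-versus-leg ambiguity is the weaker part.

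**Step 2. Reproduce the plan's sample size.** Inputs from protocol section 7.4 and SAP section 4.3: mean change 1.79, SD 1.83, placebo effect 40%, two-sided alpha 0.05, power 90%.

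- Difference: 1.79 × (1 − 0.40) = 1.074, stated as 1.07.
- Per arm: n = 2 × (1.960 + 1.282)² × 1.83² / 1.07² = 61.5, rounded up to 62. The plan's figure reproduces.
- Standard error of the difference at 62 per arm: 1.83 × √(2/62) = 0.329.
- Power: Φ(1.07/0.329 − 1.96) = 90.2%. The exact t-test gives 89.8%.

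**Step 3. Illustrate dilution.** The documents give no figure for how much unrelated pain enters the score or how much foot pain is left out. Assume that a share p of the planned difference is lost and that the SD stays at 1.83. The difference becomes 1.07 × (1 − p), and the power formula is that of Step 2.

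| Assumed p | Difference | Power at 62 per arm (normal approximation) | Power (exact t) |
|---|---|---|---|
| 0 | 1.07 | 90.2% | 89.8% |
| 10% | 0.963 | 83.4% | 82.8% |
| 20% | 0.856 | 74.0% | 73.4% |
| 30% | 0.749 | 62.5% | 61.8% |

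If the item added only noise, with the difference kept at 1.07, an assumed SD of 2.0 would give 84.6% and an SD of 2.2 would give 77.3% (normal approximation).

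**Step 4. Direction.** Both arms answer the same item under blinding and randomization. Unrelated pain is expected equally in the two arms, so it adds variance or shrinks the difference. It does not favor active or sham.

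**The case against.** The strongest defense is that the item works in context:

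- Subjects are selected for at least 6 months of daily, symmetrical neuropathic pain.
- Exclusions 2, 5, 22, 24, 26 and 27 remove much competing pain at entry, including recent claudication, non-diabetic neuropathy, mononeuropathy, residual surgical pain and arthropathy painful on walking.
- Subjects are trained on the diary at Screening and reminded at Enrollment. The companion daily question concerns analgesics for neuropathic pain.
- The full ePRO screen is not in the documents, so a heading that supplies the attribution cannot be ruled out.
- The NeuroQoL text explains foot problems by reference to the lower extremities, so the protocol uses these regional terms loosely.

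Much of this stands, and it limits the likely size of the problem. It does not remove the disagreement between sections 3.12.1, 3.4 and 4.2. The exclusions act at entry and do not cover leg pain that starts during 120 days of treatment.

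The defense is also right about the arithmetic. The 1.79 ± 1.83 comes from an earlier trial whose item wording is not given. If that wording was similar, 1.07 may already contain some dilution. In addition, a subject who reads the item literally and has only sole pain would tend to fail the entry threshold, and so would not be followed on the wrong score.

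A reader might go further and infer that the NPRS fails to measure the stated pain at the treated site. The documents do not support that: the stated construct is pain in the lower extremities, not in the soles alone, and an under-specified item is not shown to miss it. A reader might also infer that Screening and diary ratings measure different things. The Screening item is not quoted, so this is possible but unproven.

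**Conclusion.** The inconsistency is real. The one quoted item behind the primary endpoint lacks the neuropathic attribution that the protocol gives to the same score elsewhere, it leaves the place of the feet open, and the SAP does not settle either matter. The consequence is possible noise or dilution, meaning lost power, and not bias toward either arm.

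The size is unknown. The fall from 90% to about 83%, 74% or 62% rests on an assumed loss of 10%, 20% or 30% of the effect, an unchanged SD and 62 evaluable subjects per arm. It shows sensitivity and is not an estimate.

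It would also be too strong to say that a null result could not be interpreted. The NeuroQoL pain domain and the PGI items that name the neuropathy give a partial cross-check. This is a should-fix: the correction is cheap and settles what the primary endpoint measures, but the documents do not show that the trial fails without it.

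**What to change.** Reword the diary item in protocol section 3.12.1 to agree with sections 3.4 and 4.2. It should ask about pain from diabetic neuropathy and state that the region is the lower extremities including the feet. The exact phrasing is for the sponsor to choose. Use the same item at Screening, in the run-in, throughout Part A and in the Part B diary weeks, and quote it in the SAP beside the endpoint definition. If the deployed ePRO screen already carries the attribution, correct the protocol text to show the full screen.

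The cost is one protocol sentence, one ePRO screen text and one line in the SAP, with no added visits or subjects. If enrollment has begun, keep one wording within each subject so that baseline and Month 4 stay comparable, and record which version each subject used.

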3.12.2 Secondary Efficacy Assessments

NeuroQoL

The NeuroQoL is a validated 29 question assessment tool that measures the effects of diabetic peripheral neuropathy and its complications on an individual's quality of life. Subjects are asked about the effect their foot problems may have on their daily life and well-being in the past 4 weeks, with "foot problems" meaning lost or reduced feeling in the lower extremities, pain discomfort, and in some cases unsteadiness while walking or standing. The questionnaire will be completed by the

35

subject at the Enrollment Visit, Month 2, Month 4, Month 8, and Month 12 visit (Day 361).

Skin Perfusion Pressure

Vasamed Sensilase PAD-IQ measures the perfusion pressure (in mmHg) of microcirculation using a laser Doppler sensor. SPP uses the reactive hyperemia to assess capillary health in specific angiosomes. Two previous trials were conducted in patients with painful peripheral diabetic neuropathy showing an increase in circulation (pressure) from baseline.

The patient lies down in supine position and remains silent and still. The Laser Sensor Assembly (LSA) is inserted into the LSA Placement Guide and the optical sensor window is oriented toward the skin on the foot. A cuff is positioned so that the LSA is centered on the bladder both horizontally and vertically. The pressure of the cuff is then automatically increased to a pressure necessary to occlude blood flow and then released at a controlled rate and a measurement of the pressure in the angiosome is made. Skin Perfusion Pressure- SPP is the pressure required for restoring microcirculatory blood flow following release of carefully controlled occlusion. Two measurements are obtained per foot; one on the dorsal aspect of each foot in the distribution of the dorsalis pedis artery angiosome and on the plantar aspect of each foot in the distribution of the lateral plantar artery angiosome. SPP will be conducted at the Enrollment Visit to obtain a baseline value and at months 2, and 4. An increase in SPP would be considered clinically meaningful.

Sural Nerve Conduction Studies (NCS)

Sural Nerve Conduction Studies (NCS) assess large myelinated axons. Using the NC-stat[®] DPNCheck[®], the subject will assume a comfortable position so that their right or left leg is visible (that the subject's outer ankle bone and Achilles tendon are visible). The patient preparation pad is then used to thoroughly clean the subject's outer lower leg and ankle bone area to remove any residue. The subject's lateral malleolar (ankle) bone is then identified to align the anode and cathode just behind with the cathode just adjacent to the middle of the ankle bone. The device is aligned on the calf pressing firmly down on the foam to ensure contact on either side of the calf. The sural nerve conduction velocity and amplitude will be recorded. The test will then be repeated on the opposite leg. NCS will be collected at the Enrollment Visit to obtain a baseline value and at Days 121 (month 4) and 361 (month 12). An increase in velocity and/or an increase in amplitude would suggest DPN improvement.

Quantitative Sensory Testing (QST)

Quantitative Sensory Testing (QST) for thermal sensation assesses small diameter unmyelinated and lightly myelinated axons. QST is a noninvasive technique providing an easy to use, validated measure of warm, cool, and heat pain thermal sensory thresholds.

The Thermal Stimulator is placed on the surface of the skin on the dorsal aspect of the foot. The Thermal Stimulator is held in place on the foot by a Velcro strap, which wraps around the subject's foot.

Contact thermal stimulation will be delivered using the Medoc Ltd. Q-Sense system. A Thermal Stimulator probe ("thermode") is placed on the surface of the skin on the dorsal aspect of the foot in the distribution of the superficial branch of the distal fibular (peroneal) nerve. The probe is held in place by a Velcro strap, which wraps around the subject's foot. Using a Patient Response Unit (PRU), the subject presses a button to identify their response to the delivered thermal stimulation. This is done by successful trials to assess cool sensation threshold (CS), warm sensation threshold (WS) and heat pain threshold (HP) modalities using the method of Limits. Within the cool and warm sensation modalities, the trial is repeated 4 times on each foot and 3 times on each foot for heat pain threshold modality. The cool thermal testing should be conducted prior to the warm and heat pain thermal testing.

Heat-Pain threshold tests a subject's ability to determine when a stimulus begins to feel painful, not hot, in order to develop a pain perception profile. At any point during testing, the subject can choose to discontinue further testing of the heating stimuli. The entire study will last between 5-10 minutes.

QST will be performed at the Enrollment Visit to obtain a baseline value and at the Day 121 Visit (Month 4), Day 240 Visit (Month 8), and Day 361 Visit (Month 12).

Patient Global Impression (PGI)

PGI is a 3-question questionnaire assessing the subject's interpretation of their painful diabetic neuropathy as well as overall health on an 11-point numerical rating scale (NRS). PGI allows subjects to integrate, into three questions their overall evaluation of their status, the different aspects of their overall diabetic neuropathy in their legs, overall health, and overall status compared to the start of the study. It is important to note that an 11-point global scale is common and considered a valid

approach; however, the specific wording for the questionnaire in this trial has not been validated.

In the first question, subjects will be asked to circle the number on an 11-point scale that best describes their overall status of their diabetic neuropathy in their legs over the past week ("How would you rate the overall status of your diabetic neuropathy in your legs over the past week?"). Subjects are then asked to circle the number on an 11-point scale that best describes their overall health over the past week ("How was your overall health over the past week?"). The third question assesses change since the start of the study on a 7-point scale ("Since the start of the study, how has your diabetic neuropathy in your legs changed?"), and to score it as either very much worse, much worse, minimally worse, no change, minimally improved, much improved or very much improved. PGI will be collected in the clinic at Months 1, 2, 3, and 4 during the 120-day treatment period and at Months 8 and 12 during the open label extension period. PGI serves to anchor within-subject changes in overall status during the course of treatment.

